8.0 LABORATORY/DATA ANALYSIS

Laboratory specimens will not be collected.

9.0 STATISTICAL CONSIDERATIONS

Demographics, baseline and treatment characteristics will be summarized for the study population. Descriptive statistics for baseline characteristics will be prepared for the two treatment groups for all randomized subjects. Continuous variables will be summarized using the number of subjects with data (n), mean, standard deviation, median, minimum and maximum. Chi-square statistics and Wilcoxon rank sum tests will be used to evaluate baseline differences between the arms for categorical and continuous variables respectively.

An interim data analysis will be performed after 40 subjects are enrolled.

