4.0 ELIGIBILITY

Inclusion Criteria:

1. Patients 18 years of age or older.
2. Have symptomatic persistent AF (i.e., a sustained episode lasting more than 7 days).
3. Undergoing ablation for the first time.

Exclusion criteria:

1. Paroxysmal AF
2. Sustained atrial fibrillation lasting more than 3 years
3. Left atrial diameter of 60 mm or greater
4. Severe Pulmonary hypertension

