7.0 SPECIMEN/DATA COLLECTION/PROCEDURES

The investigators and study staff will obtain the necessary data during the ablation procedure, from electronic and paper medical records and monitoring devices. The information will be entered in a secure database with access limited only to study personnel. No specimens will be collected.

Data will be collected at baseline, during the ablation procedure and at each follow-up visit.

Baseline - Medical history, demographics, height, weight, BMI, cardiac medications, creatinine and 12-lead ECG.

Procedure - Ablation procedure details, medications administered, and adverse events.

Pre-discharge – Cardiac medications, arrhythmia events, adverse events.

Follow-up – In-Clinic/Telephone Visits -

The study requires total of 4 follow-up visits at (months 1, 3, 6 and 12) that can be completed either by telephone or in doctor's office. Telephone contact will last approximately 10 minutes each. Following assessments will be collected.

- Current concomitant medication documentation.
- ECG Recording – will be collected only if participant had ECG done at their own doctor's office or if the site has provided the ambulatory event monitor after the procedure to collect ECG recordings,
- Documentation of any adverse events/ serious adverse events occurring since the previous evaluation. All clinically significant adverse events should be carefully documented by the research staff using the adverse event data forms.

If a clinic visit occurs as part of the subject's regular medical care during the specified follow-up window, the follow-up assessment may be conducted during this visit, and no separate telephone contact is necessary.

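### Do significance tests on baseline characteristics, and a baseline list that omits left atrial diameter and AF duration, require a change to the plan?

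*Protocol*

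**What the plan says.** Section 9.0 plans two things for the baseline data. The first is a descriptive table: "Descriptive statistics for baseline characteristics will be prepared for the two treatment groups for all randomized subjects". The second is a set of tests: "Chi-square statistics and Wilcoxon rank sum tests will be used to evaluate baseline differences between the arms", with chi-square for categorical and Wilcoxon for continuous variables. The section says nothing about what is to be done with the resulting p-values, and nothing for or against covariates in the outcome analysis.

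Section 7.0 lists the baseline items as "Medical history, demographics, height, weight, BMI, cardiac medications, creatinine and 12-lead ECG". Medical history is not broken down further. The same section says that data also come from the patients' medical records.

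Section 4.0 sets limits on two quantities that the list does not name. Patients are excluded for "Left atrial diameter of 60 mm or greater" and for "Sustained atrial fibrillation lasting more than 3 years", and the qualifying AF episode must have lasted more than 7 days. Section 6.0 gives 100 patients in two groups of 50.

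**The concern.** If allocation is sound, any baseline difference between the arms is due to chance. A p-value for that difference answers no open question, and it does not show whether the difference matters for the outcome. A trivial imbalance can be significant and a sizeable one in an important variable can be missed. If significant variables were then put into the outcome model, the final model would depend on the data.

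The baseline list makes this look worse. Two quantities that the protocol considers important enough to restrict entry are not named there. If they were not recorded, they could be neither shown by arm nor adjusted for, and in a trial of 100 patients chance imbalance in a prognostic variable is a fair worry. What would be at stake is the credibility of the one-year comparison and some of its precision.

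**Working it through.** The protocol gives no alpha, power, effect size or event rate, so there is no stated figure to reproduce. The calculations below are illustrations with an assumed two-sided alpha of 0.05.

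**1. False alarms among the baseline tests.** For k independent tests, P(at least one p < 0.05) = 1 − 0.95^k.

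- k = 8 (one per heading in section 7.0): 1 − 0.95^8 = 0.34
- k = 10: 0.40
- k = 20: 0.64

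Height, weight and BMI are correlated, so independence is a simplification.

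**2. Missed imbalances.** With 50 per arm, the standard error of a standardised mean difference is √(2/50) = 0.20.

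- P(chance imbalance above 0.2 SD) = 2[1 − Φ(0.2/0.20)] = 0.32
- P(chance imbalance above 0.3 SD) = 2[1 − Φ(0.3/0.20)] = 0.13
- Power of a two-sample test of means: 0.17 at 0.2 SD, 0.32 at 0.3 SD, 0.52 at 0.4 SD and 0.71 at 0.5 SD. Wilcoxon power is slightly lower (0.31 at 0.3 SD).

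Steps 1 and 2 confirm that these p-values are a poor guide to which imbalances matter.

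**3. Effect on the primary comparison.** Suppose a covariate correlates ρ with the outcome (assumed) and the arms differ by d SD. By normal approximation the unadjusted z statistic then has mean ρd/0.20 and variance 1 − ρ². Its type I error given that imbalance is:

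| ρ | d = 0.2 | d = 0.3 | d = 0.39 |
|---|---|---|---|
| 0.2 | 0.050 | 0.056 | 0.063 |
| 0.3 | 0.050 | 0.062 | 0.079 |
| 0.4 | 0.049 | 0.072 | 0.100 |

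Over repeated randomisations d/0.20 is standard normal. The mean ρd/0.20 therefore contributes variance ρ², and the total variance is ρ² + (1 − ρ²) = 1. The unconditional type I error is the nominal 0.05. Neither this nor the table depends on whether anyone prints a baseline p-value.

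**4. Precision.** With 60% freedom from arrhythmia in both arms (assumed), the 95% half-width for the risk difference is 1.96 × √(2 × 0.6 × 0.4/50) = 0.192. At 50% it is 1.96 × √(2 × 0.5 × 0.5/50) = 0.196. Removing the baseline tests leaves it unchanged. Adjustment could narrow it: by the linear-model formula 1/(1 − R²), an R² of 0.10 gives 1.11 and 0.20 gives 1.25 in effective sample size. No R² is given in the protocol, the formula is only approximate for a binary outcome, and the entry limits truncate both variables, which tends to lower their explanatory power.

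**5. Are the two values available?** Section 4.0 cannot be applied without knowing left atrial diameter and AF duration for each candidate. AF duration belongs naturally under medical history in a trial of persistent AF. Left atrial diameter fits none of the headings in section 7.0, but it must be known at entry and section 7.0 allows data to be taken from medical records.

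**The case for a change.** The strongest argument for a change concerns data capture. A statistical analysis plan can choose covariates later, but it cannot analyse a field that was never recorded, and left atrial diameter is not covered by any listed heading. Naming both items would take two database fields for values already obtained. The baseline tests are also the only hypothesis tests named in section 9.0, and the descriptive table already supplies what a reader needs.

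Part of this stands. The tests have little value, and the list could be more explicit. But the list is a set of headings rather than a case report form, and what is shown is an unnamed item, not a value that will be unavailable. Staff who screen on left atrial diameter have the number and would be expected to report it in the baseline table.

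The argument for adjustment is weaker. The protocol nowhere says that the baseline tests will select covariates or replace adjustment. It does not call either variable prognostic; an entry limit may equally reflect safety or feasibility. Whether to adjust, and for what, is commonly settled in the statistical analysis plan, so silence here is no fault.

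**Conclusion.** No change to the plan follows. The baseline tests are a common habit with little information in them: about a one-in-three chance of at least one spurious finding over 8 independent tests, and power of about one in three for a 0.3 SD imbalance, both at an assumed 5% level. They do no harm to the primary result, whose estimate, interval and unconditional error rate are the same with or without them, so deleting them brings no gain beyond tidiness. The unnamed baseline items are missing detail that the trial team will fill sensibly, because both values are needed before a patient can enter. Prespecified adjustment is a reasonable choice for the statistical analysis plan, and its possible gain of 11% to 25% in effective sample size rests on an assumed R² that the protocol does not support.

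This conclusion assumes sound allocation and that the p-values are not used to build the outcome model. The protocol gives no sign that they would be.
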